4.4. Exploratory Endpoints Analyses

[figure not shown]
CCI

CONFIDENTIAL

218350

CCI

CCI

4.5. Safety Analyses

Safety analyses are described in Section 4.3.2.

4.5.1. COVID-19 Assessment and COVID-19 AEs

Based on the study requirement, related analysis or a listing might be produced for the study if applicable.

A standardized MedDRA Query (SMQ) will be used to identify all COVID-19 AEs.

The overall incidence of COVID-19 AEs and SAEs, COVID-19 AEs leading to study intervention discontinuation, COVID-19 AEs leading to study withdrawal, and severe COVID-19 AEs will be summarized. The incidence of these events at individual PT level can be obtained from the standard AE/SAE summaries.

COVID-19 assessments (confirmed, probable and suspected diagnosis) for participants with COVID-19 AEs will be summarized.

The number and percentage of participants with concomitant vaccination (COVID-19) before and during the study will be tabulated with exact 95% CI.

4.6. Other Analyses

Not applicable.

4.7. Interim Analyses

No interim analyses are planned for this study.

4.8. Changes to Protocol Defined Analyses

No changes from the protocol defined analyses.

5. SAMPLE SIZE DETERMINATION

The **target enrollment** will be **1028 participants** (514 in the group receiving the RSVPreF3 OA investigational vaccine co-administered with FLU aQIV [Co-Ad group] and 514 in the Control group where RSVPreF3 OA investigational vaccine and FLU aQIV are administered in a sequential manner). This allows to obtain at least 924 **evaluable participants** (462 in the Co-Ad group and 462 in the Control group) for the

evaluation of the primary objectives, assuming that 10% of the enrolled participants will not be evaluable.

Participants who withdraw from the study will not be replaced.

Each objective will be evaluated with a nominal type I error of 2.5%.

Table 3 Overall power to demonstrate primary objectives: non-inferiority of the immunogenicity of the RSVPreF3 OA investigational vaccine when co-administered with FLU aQIV compared to when administered alone – assuming approximately 462 participants are available in each group

Endpoint	Standard deviation of \log_{10} concentration	Reference ratio	Non inferiority margin	Type II error	Power
FLU non-inferiority* (1-sided test with alpha=2.5%)					
GMTs HI H1N1 strain	0.6	1.05	1.5	2.5%	97.5%
GMTs HI H3N2 strain	0.6	1.05	1.5	2.5%	97.5%
GMTs HI B/Yamagata	0.6	1.05	1.5	2.5%	97.5%
GMTs HI B/Victoria strain	0.6	1.05	1.5	2.5%	97.5%
RSV non-inferiority* (1-sided test with alpha = 2.5%)					
GMTs RSV-A neutralization antibody	0.45	1.05	1.5	0.1%	99.9%
RSV non-inferiority* (1-sided test with alpha = 2.5%)					
GMTs RSV-B neutralization antibody	0.45	1.05	1.5	0.1%	99.9%
Global Type II error to show non-inferiority				~10.0%	
Global power					~90.0%

GMT = geometric mean titer; **HI** = hemagglutination inhibition; **RSV** = respiratory syncytial virus

*Pass 2019 alpha = 2.5%, Two-Sample T-Tests for Non-Inferiority Assuming Equal Variance and Equal mean

For RSV: non-inferiority limit = 0.176 (=log10[1.5]).

For each FLU vaccine strain: non-inferiority limit = 0.176 (=log10[1.5]).

Reference Ratio= 0.0212 (=log10[1.05])

Considering a potential slight interference of 1.05 in true GMTs in both groups with a common population standard error of 0.45 for the RSV-A and RSV-B neutralization antibodies and 0.6 for each of the FLU strains in \log_{10} transformed concentration, the study has at least 90.0% power to meet the primary objectives.

Nominal powers to evaluate the secondary objective

The nominal power to evaluate the non-inferiority on SCR for each of the FLU strains is above 86%, depending on the plausible rates.

Table 4 Evaluation of non-inferiority in terms of HI antibody SCR when FLU aQIV is co-administered with the RSVPreF3 OA investigational vaccine compared to FLU aQIV when administered alone assuming approximately 462 participants are available in each group for a range of plausible SCRs

N evaluable participants per group	Threshold	Plausible rates in Control group**	Type II error	Nominal Power
FLU vaccine: Non-inferiority* in terms of SCR				
462	10%	70%	8.7%	91.3%
462	10%	50%	13.9%	86.1%
462	10%	35%	11.0%	89.0%
462	10%	25%	6.1%	93.9%

SCR = Seroconversion Rate.

*Pass 2019 alpha = 2.5%, for SCR – Non-inferiority: Proportions – Two independent Proportions – Non-Inferiority Tests for the Difference Between Two Proportions.

** SCR observed in the Control group in Zoster-004 study range from 35.3% to 60.9%.

6. SUPPORTING DOCUMENTATION

6.1. Appendix 1 Study Population Analyses

A summary of the number of participants in each of the participant level analysis set will be provided.

In this multicentre global study, enrollment will be presented by country.

6.1.1. Participant Disposition

The number of participants who withdraw from the study will be tabulated by group according to the reason for drop-out. This analysis will be based on the ES and the PPS.

6.1.2. Demographic and Baseline Characteristics

The median, mean, range and standard deviation of age (in years) at first vaccination will be computed by group. The center distribution, distribution of participants in each age category (65-69 YOA, 70-79 YOA, ≥ 70 YOA and ≥ 80 YOA) geographical ancestry and sex composition will be presented. This analysis will be based on the ES, the PPS and on the **CCI**

The number and percentages of participants with medical history classified by the MedDRA Primary SOC, HLT and PTs will be tabulated by group for the ES.

6.1.3. Protocol Deviations

The number of participants enrolled into the study as well as the number of participants excluded from per protocol set (PPS) analyses will be tabulated for the total population. This analysis, also broken down by study group, will be based on the ES.

The number of participants enrolled into the study as well as the number of participants excluded from per the ES will be tabulated for the total population. This will be based on all enrolled participants.

6.1.4. Concomitant Medications

The number and percentage of participants and doses using concomitant medication (any medication, any antipyretic and any antipyretic taken prophylactically, respectively) during the 7-day follow-up period (i.e., on the day of vaccination and 6 subsequent days) and during the 30-day follow-up period (i.e., on the day of vaccination and 29 subsequent days) will be summarized by group after each vaccine dose and overall.

6.1.5. Concomitant Vaccinations

The number and percentage of participants and doses with concomitant vaccination during the 30-day follow-up period (i.e., on the day of vaccination and 29 subsequent days) will be summarized by group after each vaccine dose and overall.

6.1.6. Additional Analyses Due to the COVID-19 Pandemic

Depending on how the Covid-19 situation evolves, the SAP might be amended to reflect the analysis corresponding to Covid-19.

6.2. Appendix 2 Data Derivations Rule

This section contains standard rules for data display and derivation for clinical and epidemiological studies.

6.2.1. Attributing events to vaccine doses

The dose relative to an event is the most recent study dose given to a participant prior to the start of a given event. For example, if the start date of an AE is between Dose 1 and Dose 2, the relative dose will be Dose 1.

If an event starts on the same day as a study dose, the relative dose will be derived from the additional information provided in the case report form (CRF) using the contents of the flag indicating if the event occurred before or after study dose. If 'after study dose' is selected, the relative dose for the event will be the one administered on the start day of the event. If 'before study dose' is selected, the relative dose for the event will be the dose prior to this one.

6.2.2. Handling of missing data

6.2.2.1. Dates

When partially completed dates (i.e., dates missing a day and/or month) are used in calculations, the following standard rules will be applied:

- A missing day will be replaced by 15

- A missing day and month will be replaced by June 30th.

The following exceptions apply:

When partially completed dates (i.e., with missing day or month) are used in calculations, the following rules will be applied:

- AE start dates with missing day:
 - If the month is not the same as the vaccine dose, then the imputed start date will be the 1st of the month.
 - If the event starts in the same month as the vaccine dose, the flag indicating if the event occurred before or after vaccination (AE.AESTRTPT) will be used to complete the date. If 'after vaccination' is selected, the imputed start date will match the vaccine dose given during that month. If 'before vaccination' is selected, the imputed date will be one day before the vaccine dose given during that month.
- AE start dates with missing day and month:
 - If the year is not the same as the vaccine dose, then the imputed start date will be the 1st of January.
 - If the event starts in the same year as the vaccine dose, the flag indicating if the event occurred before or after vaccination (AE.AESTRTPT) will be used to complete the date. If 'after vaccination' is selected, the imputed start date will match the first vaccine dose given during that year. If 'before vaccination' is selected, the imputed date will be one day before the first vaccine dose given during that year.
- AE end dates with missing day: the imputed end date will be the last day of the month (30 or 31) or the study conclusion date whichever comes first.
- AE end dates with missing day and month: the imputed end date will be the last day of the year (31st of December) or the study conclusion date whichever comes first.

All incomplete concomitant medication/vaccination start/end date will follow the rules above.

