
Interval	Planned Visit Interval	Allowed Interval Range
Visit 1 (Day 1) → Visit 2 (Day 31)	30 days	30 – 37 days
Visit 2 (Day 31) → Visit 3 (Day 45)	14 days	12 – 16 days
Visit 2 (Day 31) → Visit 4 (Day 61)	30 days	30 – 37 days
Visit 2 (Day 31) → Contact 1 (Month 7)	180 days	180 – 210 days

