4. STUDY DESIGN

4.1. Overall design

Figure 1 Study design overview

AE = adverse event; N = number of participants; pIMD = potential immune-mediated disease; RSV = respiratory syncytial virus; SAE = serious adverse event

- **Type of study:** self-contained.
- **Experimental design:** Phase III, randomized (ratio 1:1), open-label, multi-country study with 2 parallel groups (see [Figure 1](#)).
- **Study groups (refer to [Figure 1](#) and [Table 6](#) for an overview of the study groups):**
 - **Co-Ad (co-administration) group:** Participants receiving the RSVPreF3 OA investigational vaccine co-administered with FLU aQIV (referred to as FLU vaccine).
 - **Control group:** Participants receiving the FLU aQIV (referred to as FLU vaccine) and the RSVPreF3 OA investigational vaccine in a sequential manner.
- **Duration of the study:** ~6 months for participants in Co-Ad group; ~7 months for participants in Control group.
- **Primary completion date:** Day 61 (1 month after the RSVPreF3 OA investigational vaccine dose in Control group).
- **Control:** active comparator, i.e., sequential administration of licensed FLU vaccine and RSVPreF3 OA investigational vaccine.
- **Blinding:** open-label. Refer to Section [6.3.5](#) for details.
- **Data collection:** standardized electronic Case Report Form (eCRF). Solicited events will be collected using an electronic diary card (eDiary). Unsolicited AEs will be collected through questioning at study visits/contacts and reported into the eCRF. See Section [8.3.2](#) for details.
- **Safety monitoring:** the study will be conducted with oversight by the project Safety Review Team (SRT). Please refer to Section [10.1.5](#) for the SRT structure.
- **Vaccination schedule:**

Co-Ad group: Participants will be receiving both the RSVPreF3 OA investigational vaccine and FLU vaccine at Visit 1 (Day 1).

Control group: Participants will be receiving the FLU vaccine at Visit 1 (Day 1) and subsequently the RSVPreF3 OA investigational vaccine at Visit 2 (Day 31).

Table 6 **Study groups and interventions**

Study Groups	Number of Participants	Age (Min-Max)	Study Interventions
Co-Ad	~514	≥ 65 years	RSVPreF3 OA investigational vaccine
			FLU aQIV
Control	~514	≥ 65 years	RSVPreF3 OA investigational vaccine
			FLU aQIV

Co-Ad = co-administration; RSVPreF3 OA = respiratory syncytial virus PreFusion protein 3 older adult

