	All inclusion/exclusion criteria defined in the protocol to be checked.	Visit 1,2,3*,4 for the control group	the condition is met.	
2020	All Pre-dose results are missing: RSV-A, RSV-B and HI for the FLU vaccine strains	Co-Ad group: Visit 1 Control group: Visit 1 and Visit 2	All	PPS for analysis of immunogenicity
2040	Administration of any medication forbidden by the protocol Use of any investigational or non-registered product (drug or medical device) other than the study interventions during the period beginning 30 days before the first dose of study interventions, or planned use during the study period. Administration of long-acting immune-modifying drugs or planned administration at any time during the study period (e.g., infliximab). Administration of immunoglobulins and/or any blood products or plasma derivatives planned administration during the study period. Chronic administration (defined as more than 14 consecutive days in total) of immunosuppressants or other immune-modifying drugs planned administration during the study period. For corticosteroids, this will mean prednisone ≥ 20 mg/day, or equivalent. Inhaled and topical steroids are allowed.	Visit 1,2 for the Co-ad group. Visit 1,2,3*,4 for the control group	From the specific visit (1,2,3* or 4) the condition is met	PPS for analysis of immunogenicity
2050	Intercurrent medical condition: Participants may be eliminated from the PPS for immunogenicity if, during the study, they incur a condition that has the capability of altering their immune response (intervent medical condition) or are confirmed to have an alteration of their initial immune status.	Visit 1,2 for the Co-ad group. Visit 1,2,3*,4 for the control group	From the specific visit (1,2,3* or 4) the condition is met	PPS for analysis of immunogenicity
2080	Participants did not comply with vaccination schedule for the control group number of days between dose 1 and dose 2 is outside [30-37 days]	Visit 2	Visit 3 for the control group	PPS for analysis of immunogenicity

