- The number of days with solicited events ongoing beyond the 7-day follow-up period (i.e., the day of vaccination and 6 subsequent days) will be tabulated for each individual solicited event using descriptive statistics (mean, minimum, Q1, median, Q3, maximum). The same computations will be done for Grade 3 solicited events.

All Analyses described above for solicited AEs will be also generated during only the 4-day follow-up period (i.e., the day of vaccination and 3 subsequent days).

- The number and percentage of participants with any unsolicited AEs during the 30-day follow-up period (i.e., the day of vaccination and 29 subsequent days) with its exact 95% CI will be tabulated by group and by Medical Dictionary for Regulatory Activities (MedDRA) System Organ Class (SOC), High Level Term (HLT) and Preferred Term (PT). Similar tabulation will be done for Grade 3 unsolicited AEs, for any causally related unsolicited AEs, for Grade 3 causally related unsolicited AEs and for unsolicited AEs resulting in a medically attended visit. The verbatim reports of unsolicited AEs will be reviewed by a physician and the signs and symptoms will be coded according to the MedDRA Dictionary for Adverse Reaction Terminology. Every verbatim term will be matched with the appropriate Preferred Term. The above analysis by dose will also be performed.

These analyses will present all unsolicited AEs, including SAEs and pIMDs (unless otherwise specified).

- The number and percentage of participants with at least one report of SAE classified by the MedDRA Primary SOC, HLT and PTs and reported after vaccine administration (Day 1) up to study end (6 months after last vaccination) will be tabulated with exact 95% CI.
- The number and percentage of participants with at least one report of causally related SAE classified by the MedDRA Primary SOC, HLT and PTs and reported after

vaccine administration (Day 1) up to study end (6 months after last vaccination) will be tabulated with exact 95% CI.

- The same tabulation will be presented for fatal SAEs.
- All SAEs will also be described in detail in a tabular listing.
- All pIMDs will also be described in detail in a tabular listing.
- All AEs/SAEs leading to study/intervention discontinuation from dose 1 up to study end will be tabulated.

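### An AE with a missing start day in the month of Control's second dose is dated past the 30-day window unless the doses are exactly 30 days apart; the same Co-Ad record is counted

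*SAP*

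**What the plan says.** SAP 6.2.2.1 has two rules for an AE whose start month is known but whose day is missing.

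- Month without a dose: "If the month is not the same as the vaccine dose, then the imputed start date will be the 1st of the month".
- Month with a dose: "the flag indicating if the event occurred before or after vaccination (AE.AESTRTPT) will be used to complete the date". If the flag is before, "the imputed date will be one day before the vaccine dose given during that month". If it is after, the event takes the date of that month's dose.

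The groups differ in the number of dosing days (Protocol 4.1). For Co-Ad: "Participants will be receiving both the RSVPreF3 OA investigational vaccine and FLU vaccine at Visit 1 (Day 1"). Control receives FLU on Day 1 and "subsequently the RSVPreF3 OA investigational vaccine at Visit 2 (Day 31"). Protocol 1.3, Table 4 gives the interval: "Visit 1 (Day 1) → Visit 2 (Day 31) 30 days 30 – 37 days". SAP 3.1.2, code 2080 uses the same limits: "number of days between dose 1 and dose 2 is outside [30-37 days"].

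SAP 4.3.2 tabulates "The number and percentage of participants with any unsolicited AEs during the 30-day follow-up period", defined as the vaccination day and the 29 days after it. SAP 6.2.1 assigns an event between the two doses to Dose 1. SAP 6.2.2.1 has no separate rule for an event lying between two study doses, and it does not hold the imputed date within the 30-day window.

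**The concern.** Dating an event to the day before a dose suits an event that preceded all vaccination. In Control, an event before dose 2 is normally a post-FLU event. The rule keeps it after dose 1 but places it as late as possible, which is usually just past the end of the dose-1 window and still before the dose-2 window.

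Co-Ad has no dose about a month after Day 1, so an identical record is dated as early as possible and is counted. An imputation rule should not give different answers by arm to the same record.

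The tables at stake are the 30-day unsolicited AE summaries (any, Grade 3, related, medically attended), by dose and overall, where Control is the reference for co-administration. SAP 6.2.2.1 applies the same date rules to incomplete concomitant medication and vaccination dates; that effect is not sized here.

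**Working it through.** **Inputs.** Dose interval k = 30 to 37 days (Protocol Table 4; SAP code 2080). The vaccination day is onset Day 1 (SAP 6.2.3.6). The window is Days 1-30 (SAP 4.3.2).

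**1. The plan's own days.** Onset day = start date - dose date + 1. Dose 2 at k = 30 is Day 31, as stated, and at k = 37 it is Day 38. The vaccination day plus 29 days gives Days 1-30, as stated.

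**2. Control record** (month of dose 2, flag before). Imputed onset = (k + 1) - 1 = Day k.
- k = 30: Day 30, counted.
- k = 31 to 37: Days 31-37, after the dose-1 window and before the dose-2 window, so in neither.

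That is 7 of the 8 allowed intervals. The exceptional extra 30 days for Control's Visit 2 (Protocol section 8) also puts the date outside.

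**3. Co-Ad record.** It is set to the 1st of the month, which is never later than the true onset. An event that truly began on Days 1-30 therefore stays in the window.

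**4. Example.** Dose 1 on 20 October 2022; AE in November, day unknown.
- Control, dose 2 on 22 November (k = 33): dated 21 November = Day 33, not counted.
- Control, dose 2 on 19 November (k = 30): dated 18 November = Day 30, counted.
- Co-Ad: dated 1 November = Day 13, counted.

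**5. Share of Control post-FLU missing-day events lost.** I enumerated dose-1 dates from 1 September 2022 to 28 February 2023 (an assumed season, 181 dates), eight intervals and true onset Days 1-30. That gives 181 × 30 = 5,430 cases per interval.

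| Interval k (days) | Lost, onset even over Days 1-30 |
|---|---|
| 30 | 0 / 5,430 = 0% |
| 31 | 2,497 / 5,430 = 46.0% |
| 37 | 1,567 / 5,430 = 28.9% |
| All eight, equal weight | 14,119 / 43,440 = 32.5% |

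Calendar 2023 gives 28,399 / 87,600 = 32.4%. If Co-Ad had the 16,672 records that fall in the dose-2 month, it would count all of them.

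**6. Other scenarios** (all assumptions; the documents give neither the onset pattern nor the actual intervals).

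| Onset pattern | Intervals equal | Half at exactly 30 days |
|---|---|---|
| Even over Days 1-30 | 32% | 19% |
| Exponential decline, 14-day scale | 19% | 11% |
| Exponential decline, 7-day scale | 11% | 6% |

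**7. Effect on the tables.** Reduction in Control post-FLU event count = missing-day share × loss. The share is assumed to be 1-5%.
- Low: 0.01 × 0.06 = 0.06% to 0.01 × 0.11 = 0.11%, or roughly 0.1%.
- High: 0.05 × 0.325 = 1.6%.

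For participants, also assume that 30% of 514 report an unsolicited AE, with one event each: 514 × 0.30 = 154. Then 154 × 0.325 × 0.01 = 0.5 and 154 × 0.325 × 0.05 = 2.5 participants, or 0.1 to 0.5 percentage points. This leans high: a participant with another counted AE stays in the any-AE row, and 32.5% is the highest of the scenarios above.

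**The case against.** The best case against the point is about size. Thirty days is the planned interval, and there the loss is zero. AEs may cluster soon after vaccination, so fewer reach the month of dose 2. The endpoint counts participants, not events. Primary immunogenicity, eDiary solicited events and the SAE and pIMD summaries to Day 183 after the last dose are unaffected, and no between-group safety test is planned. All of this stands. It limits the size but does not remove the difference between the arms.

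Three stronger readings are tempting, and the documents do not support them.

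- *Post-FLU events are charged to the RSV vaccine.* This needs the flag to be recorded relative to dose 1 while the date is taken from dose 2. SAP 6.2.2.1 anchors the date to that month's dose. SAP 6.2.1 gives an event between doses to Dose 1, and gives a same-day event flagged before the dose to the prior dose. What remains is that 6.2.2.1 does not name the flag's reference dose.
- *A third of Control's missing-day events will be lost.* That is one scenario, with even intervals and even onset.
- *The rule could hide a co-administration signal.* The undercount is in Control, so Co-Ad looks relatively worse.

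It is also fair to say that the 1st of the month is not the truth. In the 22 November example, a Control event that truly began on 19-21 November (Days 31-33) belongs outside the window, yet the 1st would bring it in. Co-Ad records already carry that error, and Protocol 10.3.7.1 limits collection of unsolicited AEs to the 30 days after vaccination, so few such records should exist.

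**Conclusion.** The point holds as a narrow flaw in a stated rule. For dose intervals of 31-37 days, a Control AE in the month of dose 2 with a missing day and flagged before is imputed out of both 30-day windows, while its Co-Ad counterpart is counted. Missing-day AEs in the month of dose 1, before any change of month, are handled alike in both groups.

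The mechanism rests only on the documents' dates and on the natural reading that the flag refers to the dose given in that month. The size rests on assumptions: the spread of actual intervals, the timing of onset and the share of missing days. Across the scenarios shown, Control post-FLU event counts fall by roughly 0.1-1.6%, and participant percentages by less. No conclusion of the trial is at risk; it is a cheap correction worth making before the safety tables are programmed.

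**What to change.** In SAP 6.2.2.1, for a missing start day in a month with a dose:

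- If the flag is before and an earlier study dose was given, impute the later of the 1st of that month and the earlier dose date, and attribute the event to the earlier dose, consistent with 6.2.1. The later-of clause prevents a date before dose 1 if both doses fall in one month.
- Keep the day-before-the-dose rule only for events before the first dose.
- State that the flag refers to the dose given in that month.

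In the example, both arms then get 1 November = Day 13. The cost is a sentence or two in the SAP and a small change to the derivation program, with no new data and no change to Co-Ad results. The downside is that a few Control events that truly began after Day 30 could be counted, as already happens for Co-Ad records.
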